| Population | 56 patients with a GI cancer malignancy with planned ≥3 months of a 5-FU- and oxaliplatin-based chemotherapy regimen. Eligibility criteria includes: 1) GI cancer (primary esophagus, gastric, pancreas, biliary, small bowel, appendix, colon, or rectal) scheduled to receive a new start of 5-FU, oxaliplatin, ± irinotecan [FOLFOX, FOLFIRINOX, FOLFOXIRI regimens] with plan for ≥3 months of therapy with the regimen, 2) age ≥18 years, 3) absolute neutrophil count >500 and platelet count >20,000, 4) not currently pregnant, 5) ability to understand and the willingness to sign a written informed consent document, 6) no baseline neuropathy from any cause, 7) no prior neurotoxic chemotherapy of any kind in the prior 3 years, 8) no planned initial dose of oxaliplatin <100% of the standard regimen-specified dose, 9) no receipt of acupuncture treatment in the prior 3 months, 10) no use of concomitant duloxetine for minimization of neuropathy, 11) no psychiatric illness/social situations that would limit compliance with study requirements. |
| Primary Endpoint | Chemotherapy-induced peripheral neuropathy as measured by the EORTC-CIPN 20. |
| Secondary Endpoints | 
 Incidence of grade 2 or higher CIPN as measured by CTCAE version 5. Severity of chemotherapy-induced peripheral neuropathy as measured by a Neuropen and tuning fork. Proportion of patients assigned to the intervention arm who complete 60% of acupuncture treatments. Incidence of pain, fatigue, nausea, oral dysesthesia, and anxiety as measured by the NCI PRO-CTCAE, Brief Pain Inventory (BPI), and CTCAE version 5. |

| | |
|-----------------------------|--|
| Type of control | Usual care + waitlist arm – receives no acupuncture during the 3-month intervention period |
| Investigation Drug | N/A |
| Dose | Acupuncture: 12 treatments with 30-minute needle retention |
| Route of administration | Acupuncture: filiform needle insertion |
| Regimen | 12 sessions of acupuncture. Acupressure training and self-treatment. |
| Trial Blinding | None |
| Treatment Groups | Arm A: Acupuncture + Acupressure Intervention with standard-of-care cryotherapy: acupuncture during chemotherapy infusion (day 1) and 5-FU pump disconnect (day 3) of each biweekly chemotherapy infusion x6 cycles (i.e. 12 acupuncture treatments over 12 weeks) + self-acupressure Arm B: Waitlist Control Arm with standard-of-care cryotherapy: 6 acupuncture sessions after the completion of the trial |

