6.1.2 Secondary Objectives

- 1: To estimate the incidence of grade 2 or higher CIPN following 3 months of acupuncture/acupressure treatment plus oral cryotherapy compared to oral cryotherapy alone.
- 2: To evaluate the severity of CIPN in GI cancer patients receiving oxaliplatin-based chemotherapy following 3 months of acupuncture/acupressure treatment plus oral cryotherapy compared to oral cryotherapy alone using objective measurement tools.
- 3: To assess the feasibility of delivering acupuncture during biweekly chemotherapy infusion and the feasibility of patient self-administered acupressure between infusions.
- 4: To evaluate the effect of oral cryotherapy with acupuncture/acupressure vs. oral cryotherapy alone in reducing pain, fatigue, nausea, oral dysesthesia, and anxiety in GI cancer patients receiving oxaliplatin-based chemotherapy.

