6.3.2 Secondary Endpoints

Incidence of grade 2 or higher CIPN as measured by CTCAE version 5.

Severity of CIPN as measured by a Neuropen and tuning fork.

Proportion of patients assigned to the intervention arm who complete 60% of acupuncture treatments.

Incidence of pain, fatigue, nausea, oral dysesthesia, and anxiety as measured by the NCI PRO-CTCAE, BPI, and CTCAE version 5.

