13.7 Adverse Event Recording Period

AEs will be monitored and recorded in study-specific case report forms (CRFs) from the time of first exposure to acupuncture. AEs with an onset date prior to the first exposure to an investigational procedure will not be recorded, except in the case of clinically significant worsening of the AE during the specified AE monitoring time frame.

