16.2.2 Secondary Endpoints

- Incidence of grade 2 or higher CIPN as measured by CTCAE version 5
- Severity of CIPN as measured by a Neuropen and tuning fork.
- Proportion of patients assigned to the intervention arm who complete 60% of acupuncture treatments.
- Incidence of pain, fatigue, nausea, and anxiety as measured by patient-reported (NCI PRO-CTCAE, BPI, oral dysesthesia) and provider-assessed (CTCAE version 5) grading scales.

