16.5 Statistical Analysis

Severity of CIPN (EORTC-CIPN-20 score) at 3 months will be summarized for each treatment arm, and treatment comparisons made via linear regression model with adjustment for baseline severity level. Adherence to acupuncture treatment among patients in the intervention arm will be described as a proportion with 95% confidence interval. Reasons for treatment non-adherence and delivered dose intensity of chemotherapy will be noted. Incidences of CIPN (grade 2 or higher), pain, fatigue,

nausea, and anxiety will be compared between treatment arms using Chi-squared or Fisher's exact tests as appropriate. As this is a pilot study, we will not have adequate power to adjust for covariates such as age, gender, and existing comorbidities.

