20.2 APPENDIX B: Study Calendar

Study Calendar

| Procedure | Screening within 14 days | Cycle 1 | | Cycles 2-3 ⁶ | | Cycle 4 ⁶ | | | Cycles 5-6 ⁶ | | End of Tx ⁷ | Waitlist control visit ⁸ |
|-------------------------------------|--------------------------|----------------|----------------|-------------------------|----------------|----------------------|----------------|----------------|-------------------------|----------------|------------------------|-------------------------------------|
| | | Day 1 | Day 3 | Day 1 | Day 3 | Day 1 | Day 3 | Day 8 ± 2 days | Day 1 | Day 3 | | |
| Physical Exam ¹ | X | X | | X | | X | | | X | | X | X |
| Medical History | X | X | | X | | X | | | X | | X | |
| Pregnancy Test | X | | | | | | | | | | | |
| CBC ² | X | X | | X | | X | | | X | | | |
| Oxaliplatin-based chemotherapy | | X | | X | | X | | | X | | | |
| Acupuncture treatment | | X ³ | X ³ | X ³ | X ³ | X ³ | X ³ | | X ³ | X ³ | | X |
| Acupressure training ^{3,4} | | X | | X | X | | | | | | | |
| Acupressure diary review | | | | X | | X | | | X | | X | |
| Cryotherapy | | X | | X | | X | | | X | | | |
| AE Assessment | | X | | X | | X | | | X | | X | X ⁹ |
| PROs ⁵ | | X | | | | X | | X ⁵ | | | X | |
| Neuropen, tuning fork | | X | | | | X | | | | | X | |
| Acupuncture Expectancy Scale | X | | | | | | | | | | | |

¹ On day 3, only vital signs are needed (a complete physical exam is not required). For waitlist control visits, this will include notation of pulse, tongue color, and any other findings considered notable to the acupuncturist

² Labs may be obtained up to 3 days prior. If lab values are below the accepted treatment thresholds, they must be repeated and above treatment parameters before treatment delivery.

³ Patients in Arm A (intervention arm) only

⁴ Acupressure retraining will be completed at the cycle 2, day 1 visit if a patient has completed <50% of the prescribed regimen

⁵ PROs for all time points: EORTC QLQ CIPN-20, NCI-PRO CTCAE, BPI, oral symptoms. At C4D8, a sub-set of the PROs will be re-administered: EORTC QLQ CIPN-20, NCI-PRO CTCAE, BPI

⁶ Study procedures will be timed with patient chemotherapy. If chemotherapy is delayed, then the acupuncture, acupressure, and standard-of-care treatments will be delayed accordingly.

[figure not shown]
⁷ See section 9.9 for a description of the permitted time range for the EOT visit.

⁸ Patients in Arm B (control arm) only

[figure not shown]

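### Objective 4: section 16.5 has no comparison for oral dysesthesia, tests the other four symptoms only as undefined, unadjusted incidences, and relies on adverse event recording whose start in Arm B is unclear

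*Combined protocol and SAP*

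**What the plan says.** **Objective and endpoints.** Secondary objective 4 (section 6.1.2) concerns the effect of the intervention "in reducing pain, fatigue, nausea, oral dysesthesia, and anxiety in GI cancer patients receiving oxaliplatin-based chemotherapy". Section 6.3.2 makes this an endpoint: "Incidence of pain, fatigue, nausea, oral dysesthesia, and anxiety as measured by the NCI PRO-CTCAE, BPI, and CTCAE version 5". The synopsis gives the same five symptoms: "Incidence of pain, fatigue, nausea, oral dysesthesia, and anxiety as measured by the NCI PRO-CTCAE, Brief Pain Inventory (BPI". Section 16.2.2 differs: "Incidence of pain, fatigue, nausea, and anxiety as measured by patient-reported (NCI PRO-CTCAE, BPI, oral dysesthesia". There, four symptoms are named, and oral dysesthesia appears only inside the bracket, as a patient-reported scale.

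**Analysis.** Section 16.5 takes the incidences of CIPN (with a grade 2 cut-off), pain and fatigue, and continues: "nausea, and anxiety will be compared between treatment arms using Chi-squared", with Fisher's exact test as the alternative. Oral dysesthesia is not in the sentence, and the grade cut-off is attached to CIPN alone. The same paragraph compares the CIPN-20 score at 3 months by linear regression adjusted for its baseline.

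**Data.** Section 10.2 schedules the patient-reported forms at baseline, 6 weeks and 12 weeks. Fatigue, nausea and anxiety use five-level items (Appendix E), pain a 0-10 rating (Appendix F), and oral symptoms six five-level items with no scoring rule (Appendix G).

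**Adverse event recording.** Section 13.7 records events "from the time of first exposure to acupuncture". The control arm, per the synopsis, "receives no acupuncture during the 3-month intervention period". The calendar (Appendix B) schedules adverse event assessment from cycle 1 day 1. Its footnote 3, "Patients in Arm A (intervention arm) only", is on the acupuncture and acupressure-training rows but not on the adverse event row.

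**The concern.** One of the five symptoms has an objective, an endpoint and its own form, but no planned comparison.

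For the other four, nothing fixes which response level counts as an event, at which visit, on which instrument, or how a patient-reported symptom already present at baseline is treated. Section 7.1.1 allows one cycle of the regimen before enrolment, so some patients may enter with symptoms. An event that can be defined after the data are seen can produce a favourable p-value by selection. Reducing a graded score to yes/no and ignoring its baseline can also lose precision, which matters at about 25 per arm.

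The provider-graded incidences depend on adverse events being recorded alike in both arms. Read literally, section 13.7 never starts recording in Arm B during the comparison period.

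**Working it through.** **1. The plan's own figure.** Section 16.3: 50 complete patients (25 per arm), 0.7 SD, one-sided 5%. The noncentrality is 0.7 × √(25/2) = 2.475. The normal approximation gives Φ(2.475 − 1.645) = 79.7%; the noncentral t (df 48) gives 78.7%. Loss to follow-up: 50/0.9 = 55.6, so 56. The stated 80% and 56 reproduce. They concern the CIPN-20 only; the plan gives no effect or power for any objective 4 symptom.

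**2. Coverage of the five symptoms.**

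| Symptom | 6.1.2, 6.3.2 | 16.2.2 | Test in 16.5 | Threshold or visit | Baseline and follow-up scores |
|---|---|---|---|---|---|
| Pain | yes | yes | yes | none | yes |
| Fatigue | yes | yes | yes | none | yes |
| Nausea | yes | yes | yes | none | yes |
| Anxiety | yes | yes | yes | none | yes |
| Oral dysesthesia | yes | as a scale only | **none** | none | yes |

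**3. What the yes/no analysis can cost.** The documents give no symptom distributions, so these are assumptions: 25 per arm, two-sided 5%, a 0.7 SD benefit (borrowed from section 16.3), and baseline correlation r = 0.3 to 0.6.

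With a share p0 of controls having any symptom, the intervention share is p1 = Φ(Φ⁻¹(p0) − 0.7). For p0 = 0.8, 0.5 and 0.3, p1 = 0.556, 0.242 and 0.110. Exact chi-squared power is 47.5%, 50.4% and 40.4%.

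For five-level items, a latent normal score was cut into five categories at both visits (10,000 simulated trials). Control probabilities were 20/30/30/15/5%, 50/20/15/10/5% and 70/12/9/6/3%. The adjusted model regresses the 12-week score on arm and own baseline score.

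| Controls symptom-free | Adjusted linear, r = 0.3 / 0.5 / 0.6 | Chi-squared on any symptom | Difference (points) |
|---|---|---|---|
| 20% | 64.3 / 70.7 / 75.7% | 46.2 / 47.1 / 48.3% | 18 to 27 |
| 50% | 51.8 / 57.6 / 60.9% | 49.0 / 51.2 / 49.8% | 3 to 11 |
| 70% | 37.4 / 40.6 / 43.0% | 39.5 / 39.8 / 40.7% | −2 to +2 |

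If 80% are symptom-free at baseline, the differences become 16 to 22, 1 to 9 and −3 to +3. Type I error of the linear model at r = 0.5 was 4.5-4.9% in these three settings.

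**4. What the undefined event can cost.** With no true effect, the same item distributions and 40,000 simulated trials, three cut-points are available (mild, moderate or severe and above) at 6 or 12 weeks, with between-visit correlation 0.3 to 0.7. Section 16.5 does not define when Fisher's test is appropriate; I assume it is used when an expected count is below 5. The chance of p < 0.05 for one symptom is:
- best of three cut-points at one visit: 8-13%;
- best of three cut-points at either visit: 14-24%.

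Both count either direction. A false claim of benefit is 4-7% and 7-12%. These are worst cases, in which the most favourable choice is always made.

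**5. Start of adverse event recording.** Section 13.7 starts at first acupuncture, and Arm B has none in the intervention period. The calendar starts at cycle 1 day 1 with no arm restriction. The two give different start points for Arm B and must be reconciled.

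**The case against.** The strongest reply is that these are short omissions in exploratory analyses of a pilot. Oral dysesthesia looks like a drafting slip, since the objective, the endpoint and the form all exist. Incidence is the sponsor's chosen endpoint in three places. Any grade is the ordinary reading of a CTCAE incidence without a threshold, section 13.1 already excludes conditions present at screening unless they worsen, and the calendar shows that events are meant to be assessed in both arms.

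Much of this stands. The provider-graded event is largely determinable once the start is settled. Pilot status excuses low power, but it does not supply an analysis for a stated objective or a definition for the patient-reported events. The remark in 16.5 on covariates concerns age, gender and comorbidities; the same paragraph adjusts the primary score for its own baseline.

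A reader might go further in four ways that the documents do not support:
- **The planned tests are invalid or biased.** They are not: an unadjusted comparison of randomised arms remains valid.
- **Incidence should give way to scores because yes/no tests always lose power.** The gain disappears when about 70% of controls are symptom-free.
- **False positives reach 20-28%.** That takes uncorrected chi-squared even at sparse cut-points, whereas 16.5 allows Fisher's test.
- **Arm B will have no adverse event data.** That follows only from 13.7 read alone; the calendar contradicts it.

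**Conclusion.** The point holds at minor to moderate severity. Three parts rest on the text alone: no comparison for oral dysesthesia, patient-reported events with no definition, and two start points for adverse event recording in Arm B. A fourth is a better use of data already collected: a baseline-adjusted score comparison, worth 18 to 27 points of power where most controls have symptoms, 3 to 11 where half do, and essentially nothing (within about 4 points either way) where 70% do not. Those gains depend on the borrowed 0.7 SD and the assumed distributions and correlations. The false-positive ranges depend on the assumed distributions, the expected-count rule for Fisher's test and worst-case selection for a single symptom. The primary analysis and the sample size are not touched.

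**What to change.** 1. Add oral dysesthesia as a symptom in 16.2.2 and to the comparisons in 16.5. State a scoring rule for the six-item form, for example the sum of items coded 0 to 4 (range 0 to 24).
2. Keep the planned incidence comparisons. Add to 16.5 one comparison per symptom of the 12-week score: BPI worst pain, the oral symptoms score, and PRO-CTCAE worst severity for fatigue, nausea and anxiety. Use the linear regression already planned for the CIPN-20, on arm and own baseline score, with 95% confidence intervals. Label these exploratory and without multiplicity control. Any cycle 4 day 8 analysis is descriptive.
3. Before the data are seen, fix for each symptom incidence one threshold, one visit or period, one instrument and one rule for symptoms present at baseline.
4. Reconcile 13.7 with Appendix B so that adverse event recording starts at the same point in both arms.

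**Cost.** Wording and a little analysis; no new visits, forms or patients. Five more exploratory tests are added: if independent and with no effect, the chance of at least one p < 0.05 among them is 1 − 0.95⁵ = 23%, hence the label. The 12-week scores come from a late-cycle visit, ideally 14 days after day 1 of the last cycle (section 9.9), with 24-hour recall for pain and 7-day recall for the PRO-CTCAE items. They can miss early-cycle symptoms. The oral form recalls two weeks and is less affected.

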16.6 Ethnic and Gender Distribution Chart

Projected Target Accrual
 ETHNIC AND GENDER DISTRIBUTION CHART

| TARGETED / PLANNED ENROLLMENT: 60 | | | |
|---|--------------|-------|-------|
| Ethnic Category | Sex / Gender | | |
| | Females | Males | Total |
| Hispanic or Latino | 2 | 3 | 5 |
| Not Hispanic or Latino | 21 | 30 | 51 |
| Ethnic Category Total of All Subjects* | 23 | 33 | 56 |
| Racial Categories | | | |
| American Indian / Alaska Native | 0 | 1 | 1 |
| Asian | 2 | 4 | 6 |
| Native Hawaiian or Other Pacific Islander | 0 | 0 | 0 |
| Black or African American | 1 | 2 | 3 |
| White | 18 | 23 | 41 |
| More Than One Race | 2 | 3 | 5 |
| Racial Categories: Total of All Subjects* | 23 | 33 | 56 |

17.0 INVESTIGATOR OBLIGATIONS

The PI is responsible for the conduct of the clinical trial at the site and is responsible for personally overseeing the treatment of all study subjects. The PI must assure that all study site personnel, including sub-Investigators and other study staff members, adhere to the study protocol and to all applicable regulations and guidelines regarding clinical trials both during and after study completion.

All subjects are informed of the nature of the program, its possible hazards, and their right to withdraw at any time, and each subject signs a form indicating their consent to participate prior to receiving any study-related procedures (see Appendix B).

18.0 ADMINISTRATIVE AND REGULATORY CONSIDERATIONS

18.1 Pre-Study Documentation

The following documentation will be filed prior to initiation of the trial: curricula vitae of the PI and all Sub-Investigators; copy of the correspondence from the IRB/EC indicating approval of the protocol and Informed Consent Forms, signed by the IRB/EC chairperson or designee; an IRB/EC membership list containing the names and occupations of the IRB/EC members; copy of the Informed Consent Forms that were reviewed and approved by the IRB/EC.

18.2 Study Site Training

Before initiation of the study, the PI or her designated representatives will review and discuss the following items with the Investigator and clinic staff: the protocol, study procedures, record keeping and administrative requirements, drug accountability, AE reporting, Good Clinical Practice guidelines, CRF/eCRF completion guidelines, monitoring requirements, and the ability of the site to satisfactorily complete the protocol. Additional documents with instructions for study compliance and CRF/eCRF completion will be provided.

18.3 Documentation

The PI and study staff will maintain a comprehensive and centralized filing system containing all study-related documentation. These files must be suitable for inspection by any applicable regulatory agencies/competent authorities at any time, and should consist of the following elements: subject files (complete medical records, laboratory data, supporting source documentation, and the Informed Consent); study files (the protocol with all amendments, copies of all pre-study documentation, and all correspondence between the Competent Authorities, IRB/EC, etc.).

18.4 Access to Source Data

The PI will permit applicable regulatory authorities to monitor the study as needed. The CRF/eCRF and related source documents will be reviewed in detail by applicable regulatory authorities as needed. Only original source documents are acceptable for review. This review includes inspection of data acquired as a requirement for participation in this study and other medical records as required to confirm information contained in the CRF/eCRF, such as past history, secondary diagnoses, and concomitant medications. Other study records, such as correspondence with Competent Authorities, and IRB/EC and screening logs will also be inspected. All source data and study records must also be available for inspection by representatives of regulatory agencies.

18.5 Data Collection

Data will be collected and stored in an electronic database. Any changes or corrections made to the CRF/eCRF must be subsequently reviewed and signed by the PI. All data fields in the CRF/eCRF must be completed.

18.6 Protocol Interpretation and Compliance

The procedures defined in the protocol are carefully reviewed by the PI and his/her staff prior to the time of study initiation to ensure accurate representation and implementation. Protocol amendments, if any, are reviewed and implemented promptly following IRB/EC and relevant Competent Authorities approval.

18.7 Disclosure of Data/Publication

Individual subject medical information obtained as a result of this study is considered confidential and disclosure to third parties other than those noted below is prohibited. Such medical information may be given to the subject's personal physician or to other appropriate medical personnel responsible for the subject's welfare. Data generated as a result of this study are to be available for inspection on request by regulatory agencies, the Sponsor or its designee and by the IRB/EC. It is anticipated that the final results of this study will be submitted to a peer-reviewed scientific journal. Authorship on such a paper will be acknowledged with customary scientific practice.

18.8 Ethical Considerations

The Investigator agrees to conduct this study in accordance with applicable United States FDA clinical trial regulations and guidelines, applicable United States FDA clinical trial regulations and guidelines, the ICH (E6) GCP guidelines, the IRB/EC and local legal requirements and with the Declaration of Helsinki (1989). The Investigator will conduct all aspects of this study in accordance with all national, state, and local laws of the applicable regulatory agencies.

18.9 Informed Consent

The PI assumes the responsibility of obtaining written Informed Consent for each subject or the subject's legally authorized representative before any study-specific procedures are performed. Subjects meeting the criteria set forth in the protocol will be offered the opportunity to participate in the study. To avoid introduction of bias, the Investigator must exercise no selectivity with regard to offering eligible subjects the opportunity to participate in the study. Subjects or parents/legal guardians of all candidate subjects will receive a comprehensive explanation of the proposed treatment, including the nature of the therapy, alternative therapies available, any known previously experienced adverse reactions, the investigational status of the study treatment, and other factors that are part of obtaining a proper Informed Consent. Subjects will be given the opportunity to ask questions concerning the study, and adequate time to consider their decision to or not to participate.

Informed Consent will be documented by the use of a written Consent Form that includes all the elements required by FDA regulations and ICH guidelines. The form is to be signed and dated by the subject or subject's legally authorized representative and by the person who administers the consent process. A copy of the signed form will be given to the person who signed it, the original signed Consent Form will be filed with the subject's medical records, and copy maintained with the subject's study records. The date and time of time of the Informed Consent must be recorded in the source documents.

If an amendment to the protocol changes the subject participation schedule in scope or activity, or increases the potential risk to the subject, the Informed Consent Form must be amended. Any amended Informed Consent must be

approved by the IRB/EC prior to use. The revised Informed Consent Form must be used to obtain re-consent from any subjects currently enrolled in the study if the subject is affected by the amendment, and must be used to document consent from any new subjects enrolled after the approval date of the amendment.

